1.28 STEPS TO ADDRESS POTENTIAL INEQUITY OF SAMPLING ACROSS THE POPULATION

STICH3-BCIS4 recruitment aims to reflect the diversity of the UK population, and the team will develop tools that anticipate how health inequalities interact to create barriers to inclusion among underserved groups. A dedicated Patient Researcher will deliver this component of the research plan in partnership with the Leicester Centre for Ethnic Health Research (LCEHR), which has expertise in engagement with underserved communities, developing competencies in research staff, and mitigating the effects of health inequalities on research participation. To ensure effective engagement, the Patient Researcher will be employed by the LCTU and work alongside the trial management team. As well as the below, steps will be taken to provide patient facing documents in a variety of languages, as well ResearchApp™ (Healthbit ®) for direct participant data entry. Specific steps will include:

1.28.1 Engagement with Underserved Groups

A nominated Community Engagement Officer will ensure application of all the expertise of the LCEHR. They will work with the Patient Researcher to co-host workshops and advisory groups with ethnic minorities and other underserved groups to ensure their perspectives are heard in the development of recruitment techniques, paperwork, and other resources for engagement that can mitigate social, cultural, educational, or language barriers to participation.

1.28.2 Effective Community Engagement and Cultural Competence Training

To ensure the research team are culturally competent and confident with engaging with underserved groups during this trial, the LCEHR will offer training to the Patient Researcher who will then disseminate this throughout the wider research team. Modules include the use of an online toolkit that provides researchers with a framework to improve participation in research, making it more diverse and inclusive. These materials will be road tested in a national workshop, hosted by the Patient Researcher and the LCEHR and attended by participating investigators from all regional centres prior to implementation.

1.28.3 Impact

To ensure the research team are conducting research in an appropriate manner and making it inclusive, the LCEHR will support the team to conduct their own Equality Impact Assessments, by providing a toolkit and inviting the research team to drop-in training sessions to guide completion.

1.28.4 Dissemination

The Patient Researcher will work with LCEHR staff to develop an effective dissemination strategy to promote the importance of the research findings to underserved groups. This will involve workshops after trial completion to identify how best to share our results and ensure they reach all communities and to develop an advocacy strategy to make sure that the results reach each key stakeholder and decision maker, including by participating in a national stakeholder event to disseminate trial findings. In addition, to disseminate new knowledge arising from the Patient Researcher's work, they will produce outputs for investigators, researchers and participants, including a publication in a peer reviewed journal and other outputs.

1.29 WITHDRAWAL CRITERIA

The trial will adhere to the Principles for Handling end-of-participation Events in Clinical Trials Research (PeRSEVERE) (<https://perseverepinciples.org>) so that all patients are at the centre of the trial and their wellbeing considered at every step. If a patient chooses to withdraw their participation from the trial, they will be treated with respect, courtesy and will be offered the opportunity to provide feedback to the research team regarding the reason(s) for their withdrawal.

During recruitment, the investigator or designee will explain to participants that they are under no obligation to enter the trial and that they can withdraw at any time, without having to give a reason and without prejudicing their further treatment. If a patient states that they wish to withdraw, exactly what they mean by "withdraw" will be established, the extent of withdrawal will be documented in the patient notes and entered in the eCRF. The component parts of which any or all can be withdrawn are as follows:

- Withdrawal from trial assessments
- Withdrawal from procedure
- Withdrawal from self-completed questionnaires
- Withdrawal from performance of data linkage and therefore use of routinely collected data

Guidance on how to withdraw from further participation in the trial will be provided to patients in the PIS. Withdrawal from collection of outcomes through routinely collected data via data linkage should be a rare event.

1.30 DATA COLLECTION

Data collection will include all fields listed in the eCRF, completable by both the participant and the research staff.

1.31 OUTCOMES POST RANDOMISATION

Trained staff will use the Investigator portal in the ResearchApp™ (Healthbit®) to collect the following:

1. Baseline data will include patient demographics, such as age, sex, and ethnicity, as well as long term conditions and pre-operative investigations, severity of cardiac disease, risk scores (BCIS Jeopardy Scores. EuroSCORE II), revascularisation procedures, completeness of revascularisation, defined as change in BCIS-JS from baseline.
2. Mortality will be ascertained in UK participants through ONS data access request.
3. Outcomes until hospital discharge:
 - a) Unplanned mechanical circulatory support defined as the need for IABP, ventricular assist device or ECMO postoperatively.
 - b) New onset renal failure requiring renal replacement therapy (excluding dialysis during cardiopulmonary bypass (CPB)).
 - c) New focal neurological deficit (stroke) lasting more than 24 hours confirmed by clinical assessment and brain imaging.
 - d) Infection: defined as septic shock with positive blood cultures; pneumonia defined as autopsy diagnosis or roentgenographic infiltrate and at least two of the following three criteria: fever, leukocytosis, and positive septum culture; and/or deep sternal or leg wound infection requiring intravenous antibiotics and/or surgical debridement.
 - e) Bleeding requiring surgical or percutaneous intervention.
 - f) Length of stay in the Intensive Care Unit (ICU) readmissions and hospital (time to discharge from acute care after index hospitalisation; this includes time to discharge from satellite acute care units) and Days Alive and Out of Hospital at 6 months.
4. Clinical effectiveness and adverse outcomes post discharge will be ascertained using HES data obtained from NHS Digital using Primary Diagnostic International Classification of Diseases, Tenth Revision (ICD10) codes as previously described (8). ONS data will be used for ascertainment of mortality. NHS numbers will be used to submit ONS/NHS Digital data access requests by the LCTU after last participant/last visit in the UK arm.

For the primary outcome, the following HES codes will be used:

- a) All-cause mortality (ICD10): (dismeth = 4) OR (a linked record in ONS death registry). Follow-up begins the day after operation date.

- b) Cardiovascular hospitalisation and hospitalisation admission after the index admission with ICD10: I00 to I99 (which encompass all the cardiovascular diagnoses) as the *primary* diagnostic code.

HES codes for all pre-specified clinical outcomes, severe adverse events of interest will be specified in the Statistical Analysis Plan (SAP).

5. Disease-specific PROMS, including the clinical summary scores of the Kansas City Cardiomyopathy Questionnaire (KCCQ) and the overall summary scores of the Seattle Angina Questionnaire-7 (SAQ-7) will be ascertained at baseline and discharge, and then at follow-ups at 3 months, 6 months, and every 6 months thereafter using telephone / ResearchApp™ (Healthbit®). Where related to baseline, relevant measures will be performed after consent and prior to randomisation.
6. Resource use data, productivity loss, and EQ-5D-5L will be captured at baseline, and thereafter at 3, 6 and 12 months and then annually thereafter. Participants will have the option of either remote data capture using the Participant Portal to ResearchApp™ (Healthbit®), or if preferred, the Investigator Portal with research staff in person during enrolment and hospital stay, or by post or telephone follow-up post discharge in survivors identified from NHS SPINE.

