9. The number of total (first and recurrent) cardiovascular hospitalisations and heart failure hospitalisations, defined as a count and calculated as the sum of all episodes of hospitalisation with cardiovascular or heart failure cause.
10. Kansas City Cardiomyopathy Questionnaire (KCCQ), derived clinical summary score as a continuous measure collected at discharge and then 3 months and 6 months, and every 6 months thereafter by telephone / ResearchApp®
11. Seattle Angina Questionnaire-7 (SAQ-7), derived overall summary score as a continuous measure collected at discharge and then 3 months and 6 months, and every 6 months thereafter by telephone / ResearchApp®.

1.18 ADVERSE EVENTS OF SPECIAL INTEREST (AESI) WITHIN 30 DAYS OF PCI OR CABG

The following will be collected as AESIs within 30 days of PCI or CABG with the aim of providing reportable data to the Data Monitoring Committee (DMC) at regular meetings ahead of HES data being available.

1. Stroke.
2. New onset renal failure requiring dialysis.
3. Unplanned mechanical circulatory support (intra-aortic balloon pump (IABP), Impella, venoarterial extra corporeal membrane oxygenation (VA ECMO)).
4. Major bleeding requiring reoperation or rehospitalisation.
5. Major vascular complication requiring interventional radiology or surgical intervention.
6. All-cause mortality.

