6. Where patients have one or more chronic total occlusions supplying viable myocardium, the participant should only be enrolled if the necessary expertise in CTO-PCI is available, if the Heart Team consider the risk/benefit balance favours CTO intervention.

7. Staging PCI is permitted where the cardiologist feels that this is in the patient's best interest, but the intention to stage must be documented at the first procedure.
8. Mechanical circulatory support should be reserved for bailout in case of mechanical complication of the PCI or developing cardiogenic shock, unless new evidence arises during the course of the trial to indicate benefit to routine use.

Details of physiological, intracoronary imaging, and advanced percutaneous methods will be recorded in the CRF as will mechanical circulatory support.

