1.33 EXPECTED SERIOUS ADVERSE EVENTS

The risk of intervention is not negligible. In the STICH trial, participants with ischaemic left ventricular dysfunction undergoing CABG had 5% mortality at 30 days post-surgery. In contrast, the peri-procedural risk of death following PCI should be less, although the overall burden of SAEs may be similar. In the SYNTAX trial (22) for example, the rate of Major Adverse Events at 30 days was the same in both CABG and PCI groups (only 7% of participant in this trial had iLVSD). However, with time, recurrent symptoms and repeat revascularisation are typically higher in the PCI treated patients, meaning that freedom from death or revascularisation is lower. This is evident in the Kaplan Meier curves in Figure 3, where the CABG curve (blue) is initially lower, but then crosses the PCI curve (red) after 3-6 months.

[figure not shown]

Figure 3 Freedom from death or cardiovascular hospitalisation in people with heart failure undergoing CABG or complex PCI in England 2013-2018, or matched to the STICH cohort (8)

However, other trials have identified important differences in early expected adverse events following both PCI or CABG (32). These include the risk of stroke, severe acute kidney injury (AKI), unplanned mechanical circulatory support for low cardiac output, major bleeding requiring intervention, or vascular complications requiring intervention. Along with early deaths, this information may be important for future patients with iLVSD who are deciding whether to undergo PCI or CABG. These early events may also be used by governance committees to establish whether there are any clinical differences in the number of these events versus expected event rates in normal practice. For this reason, we propose to collect the following SAEs occurring within 30 days of the date of surgery or the date of the first index PCI procedure, for review by governance committees.

1. Stroke
2. New onset end-stage renal failure defined as requiring dialysis
3. Unplanned mechanical circulatory support (IABP, Impella, VA ECMO)
4. Major bleeding requiring reoperation or re-hospitalisation
5. Major vascular complication requiring interventional radiology or surgical intervention
6. All-cause mortality

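### Early bleeding, renal and circulatory-support events are defined inconsistently across the summary, 1.18, 1.31, 1.33 and Table 1, and the DMC's bleeding item misses some bleeds treated percutaneously

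*Protocol*

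**What the plan says.** The protocol carries two overlapping sets of early events.

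- **30-day list** (summary, 1.18, 1.33). It runs for 30 days from surgery or the first index PCI. Under 1.34 sites enter it in the eCRF, expected within a week, and the DMC sees it every 12 months by allocation. Under 1.56 these are the only safety events the DMC receives.
- **In-hospital list** (1.31 item 3). Trained staff collect it until hospital discharge.

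Bleeding is "Major bleeding requiring reoperation or rehospitalisation" in 1.18, with the same content in 1.33 and the summary. In 1.31 item 3(e) it is "Bleeding requiring surgical or percutaneous intervention".

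Renal failure in 1.18 is new-onset failure needing dialysis. In 1.33 and the summary it is "New onset end-stage renal failure defined as requiring dialysis". In 1.31 item 3(b) it is failure needing renal replacement therapy, with dialysis during cardiopulmonary bypass excluded.

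Circulatory support in 1.33 is "Unplanned mechanical circulatory support (IABP, Impella, VA ECMO"), with no timing condition, and 1.18 agrees. In 1.31 item 3(a) it is "Unplanned mechanical circulatory support defined as the need for IABP, ventricular assist device or ECMO postoperatively". Section 1.27.2 item 8 says of the PCI arm: "Mechanical circulatory support should be reserved for bailout in case of mechanical complication of the PCI or developing cardiogenic shock". Table 1 footnote 4 starts event capture at the start of surgery in its first sentence and at the start of the index procedure in a later one.

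**The concern.** The trial compares an operation with a catheter procedure, so an early-event definition should be equally easy to meet in either arm. Two terms here belong to surgery: *reoperation* in the 30-day bleeding item and *postoperatively* in the in-hospital support item. After PCI there is no operation to repeat, and support used as bailout may be needed during the procedure itself.

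The wording matters because little downstream would correct it. Sites enter the events prospectively, the trial is open label, and 1.32 plans no adjudication. Section 1.47 summarises the adverse events that meet the reporting criteria set out earlier, so those criteria decide what is counted. Section 1.33 says the information may matter to future patients choosing between PCI and CABG.

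**Working it through.** No figure in the protocol depends on these definitions, so there is nothing to reproduce. The check sets the passages side by side.

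**1. Bleeding**

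| Case | 30-day item 4 | 30-day item 5 (vascular) | 1.31 item 3(e) |
|---|---|---|---|
| CABG, chest reopened for bleeding | counts | not needed | counts |
| PCI, major access-site bleed treated by interventional radiology, same stay | fails | counts as a vascular complication | counts |
| PCI, pericardial bleed drained percutaneously, same stay | fails: no reoperation, no rehospitalisation | not clearly covered | counts |
| CABG, collection drained percutaneously, same stay | fails for the same reason | not clearly covered | counts |

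The gap is a same-stay bleed treated percutaneously that is not a major vascular complication. It is a gap against the list's own purpose, because the paragraph introducing the list in 1.33 speaks of major bleeding that requires intervention, which is wider than item 4. This is the one definitional gap of the three that clearly removes events from what the DMC sees.

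**2. Renal failure**

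| Place | End-stage label | Treatment criterion | Bypass exclusion |
|---|---|---|---|
| 1.18 | no | dialysis | no |
| 1.33 and summary | yes | dialysis | no |
| 1.31 item 3(b) | no | renal replacement therapy | yes |

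Sections 1.18 and 1.33 describe the same 30-day list and disagree on the label. The introduction in 1.33 gives the concern as severe acute kidney injury, which end-stage failure does not describe. The bypass exclusion can matter only where bypass is used, so that difference concerns CABG.

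**3. Circulatory support**

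| Place | Timing |
|---|---|
| 1.18, 1.33, summary | none beyond the 30-day window |
| 1.31 item 3(a) | needed postoperatively |
| Table 1 footnote 4 | from start of surgery; then from start of index procedure |

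The device names overlap, since an Impella is a ventricular assist device. Timing is the main difference. Support that starts and ends within the procedure counts under 1.18 and 1.33 and falls inside the footnote's capture period, but does not meet 3(a).

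**4. Can an effect on the contrast be sized?**

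For support, let *s* be the share of supported participants whose support is confined to the procedure. On a strict reading of 3(a),

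CABG:PCI ratio under 1.31 = ratio under 1.18 × (1 − s_CABG) / (1 − s_PCI).

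The protocol gives neither share. Three assumed pairs show the range:

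- s_PCI = 0.8, s_CABG = 0.5: factor 0.5 / 0.2 = 2.5
- equal shares: factor 1
- s_PCI = 0.5, s_CABG = 0.8: factor 0.2 / 0.5 = 0.4

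The factor falls on either side of 1 depending on the assumption, so neither size nor direction follows from the documents.

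For bleeding, the nearest figure is in 1.58.4: 3.2% major bleeding at 2 years after PCI in REVIVED. On 315 participants that is 0.032 × 315 = 10.1 over two years. It is not a 30-day figure and is not split by how or when the bleed was treated, so it cannot be turned into a count of missed events.

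**The case against.** A reader might infer that these differences bias the safety comparison and make PCI look safer. The case against that is strong.

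- The DMC receives the 30-day list, whose support item has no postoperative limit, so 3(a) does not alter what it sees.
- Nothing says that sites choose between the lists. Both are collected.
- Item 3(a) speaks of the need for support postoperatively, not of when it began. A device placed in the catheter laboratory and removed next day was still needed after the procedure and arguably counts under both lists. The same word would also drop support confined to the operating theatre.
- Vascular item 5 recovers some PCI bleeds, and a CABG participant drained percutaneously is missed by item 4 just as a PCI participant is.
- The end-stage label is followed by its own definition, requiring dialysis, so a participant with temporary dialysis meets the stated criterion.
- The safety summary is descriptive.

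All of this stands, and it disposes of the directional claim. It does not remove the inconsistencies or the gap in the DMC bleeding item.

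It may also be said that the SAP will settle the definitions. Section 1.31 does leave HES codes to the SAP, but 1.18 collects the 30-day events so that the DMC has data before HES data exist, and 1.20 excludes the 30-day events from HES ascertainment. HES codes would therefore not define what sites enter. The eCRF help text is not shown and may already be clearer than the protocol.

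**Conclusion.** The inconsistency is real and worth correcting, but limited in reach. Bleeding is the firmest part: as written, the DMC item omits same-stay bleeds treated percutaneously that are not major vascular complications, and its wording suits surgery better than PCI. The renal part is a conflict of labels within one list, plus an exclusion stated in only one place. It does not show a complication missed specifically in the PCI arm. The circulatory-support part affects the in-hospital outcome list only.

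The documents do not support a stated size, a direction favouring either arm, or a claim that the DMC's view of circulatory support is distorted. The conclusion rests on a literal reading of the protocol and on sites applying that wording. The primary outcome is unaffected.

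**What to change.** Use one procedure-neutral definition per event in the summary, 1.18, 1.31 item 3 and 1.33, and align Table 1 footnote 4:

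- **Bleeding:** requiring surgical or percutaneous intervention, or rehospitalisation.
- **Renal:** new renal failure requiring renal replacement therapy, excluding treatment during bypass. Delete *end-stage*.
- **Circulatory support:** unplanned mechanical support started during or after the procedure, with the same devices named in every place.
- **Footnote 4:** one start of capture, the start of the index procedure, in both sentences.

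State which list supplies the between-group safety summary. Because the wider bleeding wording will overlap with vascular item 5, also say whether one event may be counted under both items.

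The cost is a wording amendment and matching eCRF help text, with no new visits or assessments. Slightly more events will be counted. If participants have already been entered, check their early events against the revised wording so that one rule applies throughout.

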1.16 SIZE OF SAMPLE

STICH3-BCIS4 is a superiority trial powered for the primary outcome of survival time from cardiovascular hospitalisation and all-cause mortality. Using a time-to-event analysis to detect a HR of 0.7 with a 1:1 allocation ratio, 90% power, and a 2-sided alpha value of 0.05, a total of 414 events are required. Participants will receive a minimum of 4 years follow-up and 630 participants (n=315 in each arm) will be randomised in the UK.

The sample size is based on the following assumptions. **1.** A minimum clinically important treatment effect HR for CABG vs. PCI of 0.7 that is written within the range of treatment effects (0.63 to 0.74) observed in previous pragmatic RCTs of CABG versus PCI that have changed clinical practice (20-22). The proposed effect size was chosen as stakeholders felt that a large benefit would be required to convince clinicians of the benefits of more invasive treatment (CABG) in this high-risk population. **2.** Frequency of death or cardiovascular hospitalisation of 70% at 5 years in the PCI arm, from HES. To

calibrate this outcome, we compared the frequency of death or *heart failure* hospitalisation at 5 years in the STICH-1 matched HES cohort (42%) to event rates in both REVIVED and STICH trials (see Figure 1, from reference (8)). As heart failure hospitalisation is underestimated in HES data, the expected outcome frequencies are consistent. Coding for CV hospitalisation is more accurate and is included in the primary outcome for STICH3-BCIS4. **3.** A total study period of 89 months. **4.** An expected crossover rate of 8% typical for CABG vs. PCI trials; range 7-9%. (6, 7). **5.** Zero attrition due to the use of HES / Office for National Statistics (ONS) data for the primary outcome.

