1.17 OUTCOMES

1.17.1 Primary Effectiveness Outcome

Survival time from cardiovascular hospitalisation all-cause mortality: defined in whole days measured as time from randomisation until date of first cardiovascular hospital or death from any cause, whichever happens first. Participants who withdraw or are lost to follow-up will be censored at the date last known to be alive and free from cardiovascular hospitalisation. Participants not having an event at the time of the analysis will be censored at the last date known to be alive and free from cardiovascular hospitalisation.

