1.27 ALLOCATED TREATMENT

Revascularisation appropriateness and feasibility will be confirmed by the local Heart Team (a minimum of an interventional cardiologist and a cardiac surgeon). Revascularisation should be performed as soon as dictated by clinical urgency but no more than 18 weeks (+/- 28 days) from randomisation for elective cases or 6 weeks from randomisation for urgent/ACS cases (+/- 28 days).

Complete revascularisation of all viable myocardium is the goal for all patients. Revascularisation will be attempted on/for significant lesions in major coronary vessels/side branches as planned by the local Heart Team, with the general recommendation of stenotic/occluded vessels with diameter >1.5mm. As per contemporary ESC treatment guidelines, physiological or non-invasive functional confirmation of haemodynamic severity should be sought in any vessel that has <90% stenosis. As a measure of process, and to estimate completeness of revascularisation, the British Cardiovascular Intervention Society Jeopardy Score (BCIS-JS) will be calculated at baseline and after final stage PCI or CABG using the www.BCIS-JS.com calculator.

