1.43 ANALYSIS POPULATION

The primary analysis will be based on ITT principles with the analysis population consisting of all participants who are randomised and compared in the groups to which they were allocated regardless of treatment being received. The per-protocol (PP) population will consist of all participants who underwent revascularisation as randomised, excluding patients who had a major protocol deviation e.g., patients who crossed over, had their allocated treatment changed or discontinued by the treating physician at any time, or withdrew consent.

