1.46 PRIMARY OUTCOME ANALYSES

The primary outcome (all-cause mortality or cardiovascular hospitalization) will be calculated by measuring time from randomisation until first event or last known event-free observation during the follow-up period as defined in 1.17.1. The primary analysis of the primary outcome will compare the randomised groups using a log-rank test statistic. Survival estimates will be presented using methods by Kaplan and Meier and the adjusted hazard ratio and 95% confidence interval presented using a cox proportional hazards model (or appropriate alternative where assumptions are not met). Superiority of CABG over PCI will be declared with a two-sided p-value <0.05 on the log-rank test. A secondary analysis of the primary outcome will follow the same methodology on the per protocol (PP) population.

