1.58.5 Risks to the Trial

Randomisation with allocation concealment will utilise a centralised, web-based system. The trial is unblinded and non-adherence will be documented to assess performance bias. To mitigate this, rates of non-adherence and/or crossover observed in previous trials of PCI versus CABG are included in the sample size estimate. As this is a pragmatic trial, there are no hospital visits, imaging, blood, or other tests, that are in addition to normal care. This will mitigate attrition bias. The use of routinely collected data will mitigate against detection bias and attrition bias. The primary outcome has high accuracy of HES / ONS coding and is unlikely to be misclassified. The trial protocol will be registered in a public registry prior to enrolment of the first participant. A SAP will be published prior to data lock. The primary analysis will be by ITT and include all randomised participants unless the participant withdraws consent for follow-up. The trial will be reported as per the Consolidated Standards of Reporting Trials (CONSORT) extension for trials using cohorts and routinely collected data (48, 49).

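### The HES/ONS rule in 1.31 starts mortality follow-up the day after the operation, contradicting the randomisation time origin in 1.17.1 and 1.46 and the ITT population in 1.43

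*Protocol*

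**What the plan says.** **Time origin.** Section 1.17.1 defines the primary outcome in whole days, "measured as time from randomisation until date of first cardiovascular hospital or death from any cause, whichever happens first". Section 1.46 repeats this for the analysis: "measuring time from randomisation until first event or last known event-free observation during the follow-up period". Section 1.31 item 4 then lists the HES/ONS rules that will produce the primary outcome. Its mortality item, 4(a), ends with "Follow-up begins the day after operation date". Its hospitalisation item, 4(b), counts cardiovascular admissions later than the index admission and does not tie that admission to randomisation.

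**Gap between randomisation and procedure.** Section 1.27 allows treatment "no more than 18 weeks (+/- 28 days) from randomisation for elective cases", and 6 weeks with the same tolerance for urgent/ACS cases. Section 1.27.5 repeats both limits and allows ACS patients to be discharged and to return for the procedure.

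**Population.** Section 1.43 bases the primary analysis on "all participants who are randomised and compared in the groups to which they were allocated regardless of treatment being received". Section 1.17.1 censors those who withdraw at the date they were last known to be alive and free of the event. Section 1.58.5 reads differently: "The primary analysis will be by ITT and include all randomised participants unless the participant withdraws consent for follow-up".

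Nothing in the protocol says which statement takes precedence.

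**The concern.** Section 1.31 is the text that an analyst would turn into code when the linked data arrive. Read literally, item 4(a) does three things that an ITT analysis from randomisation does not:

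- it leaves out deaths while waiting for the procedure;
- it leaves out deaths on the day of the procedure;
- it gives no start date to a randomised patient who is never revascularised.

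All three depend on what happens after allocation, so applying the rule would be a post-randomisation exclusion. Surgery and PCI may differ in waiting time and in day-of-procedure mortality, and the groups compared would then no longer be those formed by randomisation.

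Item 4(b) adds an ambiguity. For an ACS patient discharged to return, the index admission could be the presenting stay or the procedure stay. The first reading could make the planned return for revascularisation a primary event. The second would drop any cardiovascular admission in between.

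The 1.58.5 exception matters less but is of the same kind: in an open-label trial it removes people after they know their allocation.

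**Working it through.** **1. The plan's own sample size.** Inputs from 1.16: "to detect a HR of 0.7 with a 1:1 allocation ratio", "90% power, and a 2-sided alpha value of 0.05", 8% crossover, 70% of the PCI arm with an event at 5 years. With (1.960 + 1.282)² = 10.507:

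- Without crossover, Schoenfeld: 4 × 10.507 / (ln 0.7)² gives 331. Freedman: 10.507 × (1.7/0.3)² gives 338. Neither is 414.
- With 8% one-way crossover the diluted HR is 0.7 × 0.92 + 0.08 = 0.724. Schoenfeld gives 403 and Freedman 410, within 3% of the stated 414.
- With exponential survival, uniform accrual over 41 months and a further 48 months of follow-up, 630 participants give about 426 expected events; 414 events need about 612 participants.

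The stated figures therefore reproduce closely. The calculation in 1.16 uses no operation date, so correcting the time origin leaves 414 and 630 as they are.

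**2. The statements side by side.**

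| Item | 1.17.1, 1.43, 1.46 | 1.31, 1.58.5 |
|---|---|---|
| Start of mortality follow-up | randomisation | day after operation |
| Death while waiting or on day of operation | event | not counted |
| Never has a procedure | analysed as allocated | no start date |
| Withdraws consent for follow-up | kept, censored | excluded |

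**3. How many events could fall in the gap.** Assumptions: constant hazard, the same rate in both arms, and everyone waiting exactly the stated time.

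- Composite hazard from 70% at 5 years (1.16): −ln(0.30)/5 = 0.2408 per year.
- Death hazard from 30% at 5 years (1.1, where it is an upper figure): −ln(0.70)/5 = 0.0713 per year.
- Proportion with an event in w weeks: 1 − exp(−hazard × w/52.18), multiplied by 630.

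| Wait | Deaths | Death or CV admission |
|---|---|---|
| 6 weeks (urgent limit) | 0.8%, about 5 | 2.7%, about 17 |
| 10 weeks (urgent limit + 28 days) | 1.4%, about 9 | 4.5%, about 28 |
| 18 weeks (elective limit) | 2.4%, about 15 | 8.0%, about 50 |
| 22 weeks (elective limit + 28 days) | 3.0%, about 19 | 9.6%, about 61 |

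The deaths column is what item 4(a) governs. The last column applies only if pre-procedure admissions are lost as well, which depends on how the index admission in 4(b) is read. Deaths on the day of operation are additional; the protocol gives no figure for them.

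**4. Withdrawal.** The protocol gives no rate, and 1.29 expects withdrawal from linkage to be rare. For scale, each 1% of 630 is about 6 people.

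**The case against.** The strongest defence is that the two sections that define and analyse the primary outcome agree on randomisation, that 1.43 keeps everyone, and that the odd sentence sits in a list of codes for post-discharge outcomes taken from earlier work. Section 1.31 also defers the outcome codes to the SAP. On this view no event is lost, because 1.17.1 and 1.46 would govern. This stands to the extent that the loss is conditional. It does not remove the contradiction: the sentence is a stated time origin under a primary-outcome heading, not a code left for later.

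A reader might infer more than the documents support:

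- *That all pre-procedure composite events are lost.* The sentence belongs to the mortality item; hospitalisation has its own, differently worded rule.
- *That the bias favours CABG, or that a particular hazard ratio or loss of power follows.* This needs waiting times by arm and a pre-procedure hazard. The protocol gives neither, so any such figure would come from invented inputs.
- *That this is immortal-time bias.* Restarting the clock and dropping earlier events is exclusion after randomisation, which is a selection problem.
- *That the typical wait is 22 weeks.* That is the outer elective limit; 1.27.5 encourages treatment of ACS during the index admission, so many waits should be much shorter.

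On withdrawal, 1.58.5 is a risk narrative and covers only those who withdraw consent for follow-up, not everyone who leaves some part of the trial.

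**Conclusion.** The contradiction is real and must be corrected, because it concerns the time origin of the primary comparison. Applied as written, 1.31 item 4(a) would leave roughly 5 to 19 deaths among 630 participants uncounted before the procedure, or roughly 17 to 61 composite events on the wider reading of 4(b). These counts rest on a constant hazard, the protocol's 5-year rates, and a uniform wait of 6 to 22 weeks; shorter waits give fewer. The main harm is possible bias, whose direction and size cannot be determined from the protocol, and no power figure should be attached. The 1.58.5 conflict is secondary and probably small.

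**What to change.** 1. In 1.31 item 4(a), state that follow-up begins at randomisation for all participants, whether or not a procedure takes place.
2. In item 4(b), count cardiovascular admissions from randomisation. Add an explicit rule, identical in both arms, that the planned admission or admissions for the allocated revascularisation, including documented staged PCI, are not themselves events, while other cardiovascular admissions before the procedure are. Without this rule, moving the clock could turn the planned procedure admission into a primary event.
3. In 1.58.5, remove the exception for withdrawal of consent and refer to 1.17.1: keep the participant and censor at the date last known to be alive and free from cardiovascular hospitalisation. That date is workable even where linkage consent has gone and no extract can be drawn (Table 1, footnote 5).

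The cost is a few sentences in a protocol amendment and matching SAP code. Randomisation dates are already held, and sample size and data collection do not change. Section 1.31 places the HES/ONS request after the last participant's last visit, so this can be settled before linked outcome data arrive.
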